6. STUDY DESIGN AND METHODS

i. Study Overview

This is a single center study in healthy volunteers and entail the following: initial evaluation, brain MRI and [\$^{11}\$C]ER176 PET scans for brain imaging with about half of the volunteers undergoing lung scans in the same session, and for whole-body dosimetry imaging. Healthy volunteers will be screened under screening protocol 01-M-0254. The participants must be documented to meet inclusion and exclusion criteria and sign an informed consent document. There are three phases in this protocol that follows the suggested pathway for first-in-human trial of any new PET radiotracer (Zanotti-Fregonara and Innis 2012).

Phase 0: A whole-body PET scan after [¹¹C]ER176 injection in a single healthy volunteer to confirm the radioactivity distributes across different organs and the radiation dose is safe and below the theoretical maximum for any organ in the body. This single subject will be a high-affinity binder and recruited using the consent of whole-body dosimetry.

Phase 1: Kinetic brain PET scans will be performed in healthy volunteers (n = up to 36) to quantify [11 C]ER176 binding parameters in brain. In this phase, we will recruit up to 12 subjects for each group of HABs, MABs and LABs. These subjects will have arterial lines placed for accurate measurement of input function and have a brain MRI for anatomical localization. In about half of the subjects for each group, we plan to image both brain and lungs in a single scan session lasting 120 minutes. The rationale for lung imaging is as follows.

Although the brain has a relatively low density of TSPO, it can demonstrate genotype sensitivity of binding for radioligands that have high in vivo specific binding, like [\$^{11}\$C]PBR28. However, in genotype-sensitive ligands with low in vivo specific binding, like [\$^{11}\$C]PK 11195, the sensitivity is only seen in peripheral organs that have relatively high TSPO density (Kreisl *et al* 2010). In contrast to [\$^{11}\$C]PBR28, which showed significantly lower uptake in five target organs known to express TSPO (namely brain, heart, lung, spleen and kidney), [\$^{11}\$C]PK 11195 showed significantly lower uptake only in lungs and heart of low-affinity binders (Kreisl *et al* 2010). In vitro results suggest that the newly developed TSPO ligand ER176 is not sensitive to genotype. In order to effectively evaluate the genotype sensitivity of ER176 in vivo, measuring the lung uptake will be very useful.

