12. STATISTICAL ANALYSIS

Brain imaging data will be analyzed with compartmental modeling using a nonlinear least squares analysis, graphical analysis of integration plot, and multilinear regression analyses. PET and MRI scans will be coregistered for anatomic definition of regions of interest. Percent SUV will be calculated in various brain regions. Parametric images will be created using PMOD software (PMOD Technologies Ltd., Zurich, Switzerland). The kinetic modeling will give us the [11 C]ER176 binding values, and their identifiability and stability over time. Because of inter-subject variability in pharmacokinetics and metabolism of PET radioligands, sample sizes of approximately 15 per group are required in such studies (Fujita *et al* 1999; Ichise *et al* 2003; Koeppe *et al* 1999).

In order to evaluate genotype sensitivity of [11 C]ER176 in brain we calculated the percent difference in binding values necessary to differentiate between HABs, MABs and LABs. This was based on our previous results with [11 C]PBR28 brain scans in healthy volunteers of different genotypes (Kreisl *et al* 2012). The mean V_T of HH subjects (HABs; n = 9) for whole brain was 4.5 mL/cm³ with a standard deviation of 1.4 mL/cm³. In addition, the V_T of HH subjects was 40% higher than the V_T of HL subjects. Assuming similar SD/Mean for [11 C]PBR28 and [11 C]ER176, we can calculate how much of a difference in mean V_T can be detected between genotypes. Power analysis based on V_T of HH subjects from [11 C]PBR28 scans showed that with a sample size of 10 for each binder group, a power of 80% and alpha of 0.05 the percent difference to be detected from the mean value of a HAB is 40%. That is, the difference in mean V_T between HH and other genotypes should be >40% for it to reach a statistical significance with a sample size of 10. Therefore, we require a recruitment of 12 subjects for each group (36 in total for HABs, MABs and LABs) under Phase 1 considering some withdrawals.

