Similar to brain, we calculated the percent difference in lung uptake (measured as area under time-activity curve) necessary to differentiate between HABs, MABs and LABs based on our previous results with [11 C]PK 11195 in healthy volunteers (Kreisl *et al* 2010). The mean lung uptake for [11 C]PK 11195 in HABs (n = 5) was 25.6 SUV • min with a standard deviation of 3.7 SUV • min. In addition, lung uptake was significantly higher (by 27%) in HABs than in LABs. Assuming similar SD/Mean for [11 C]PK 11195 and [11 C]ER176, we can calculate how much of a difference in mean lung uptake can be detected between genotypes. Power analysis based on [11 C]PK 11195 lung uptake in HABs showed that with a sample size of six for each binder group, a power of 80%, and alpha of 0.05, the percent difference to be detected from the mean value of an HAB is 23%. That is, the difference in mean lung uptake between HH and other genotypes should be >23% for it to reach statistical significance with a sample size of six.

In whole body imaging studies, organ time-activity curves will be obtained from the dynamic PET images, and used to calculate organ residence times. Residence time of the urinary bladder may be calculated using a dynamic bladder model (Cloutier *et al* 1973). The residence times will be used in OLINDA/EXM (http://www.doseinfo-radar.com/OLINDA.html) to obtain radiation-absorbed dose estimates. To take into account inter-subject variability, radiation absorbed doses are usually estimated from approximately 6-8 subjects (Fujita *et al* 2002; Seibyl *et al* 1994; van Dyck *et al* 1996). To also take into account possible gender differences, we propose to study approximately an equal number of

male and female subjects in the whole body imaging study. Currently we do not plan to match the genotype for subject recruitment under Phase 2 dosimetry scans but if we do find any unexpected differences between different binders from Phase 1 study, we will do at least 3 subjects for each binder group (9 subjects in total). Considering the requirement of one subject for the initial Phase 0 and any possible withdrawals, we seek a total of 11 subjects for Phase 2.

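### The lung detectable difference of 23% rests on an optimistic approximation (26% by t-test), and the PK 11195 benchmark beside it falls below 23% on the same base

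*Protocol*

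**What the plan says.** The lung power statement is in protocol section 12 (Statistical Analysis). Its inputs come from a prior PK 11195 study in healthy volunteers. Lung uptake in five HABs "was 25.6 SUV • min with a standard deviation of 3.7 SUV • min", and the ratio of SD to mean is assumed to carry over to ER176. The calculation is made "with a sample size of six for each binder group", with "a power of 80%, and alpha of 0.05", and concludes that "the percent difference to be detected from the mean value of an HAB is 23" per cent. The paragraph does not say which test, or whether one- or two-sided, produced the figure.

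Two other sentences in the paragraph matter. One gives the size of the genotype effect seen with PK 11195: "lung uptake was significantly higher (by 27%) in HABs than in LABs". The other interprets the 23%: "the difference in mean lung uptake between HH and other genotypes should be >23% for it to reach statistical significance".

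The six per group follows from section 6.i (Study Overview, Phase 1): "In about half of the subjects for each group, we plan to image both brain and lungs". For the brain, section 12 says "we require a recruitment of 12 subjects for each group".

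**The concern.** Three things in the paragraph need checking: whether 23% is right for a comparison of six with six, whether 27% and 23% can be read side by side, and whether 23% is a threshold for significance.

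Section 6.i says that the in vitro results suggest ER176 is not genotype-sensitive, and that lung uptake is a useful way to test this in vivo. Section 11 says the lung may be the more effective organ for it. A null lung result is therefore a likely outcome, and it would tend to be read as evidence of insensitivity. How far that reading is justified depends on the power statement. As written, 27% appears to clear 23%, so a reader may conclude that six per group would detect an effect of the PK 11195 size with at least 80% power.

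**Working it through.** **Inputs (section 12).** HAB mean 25.6 and SD 3.7 SUV·min, so SD/mean = 3.7/25.6 = 0.1445; n = 6 per group; power 80%; alpha 0.05; PK 11195 benchmark, HAB 27% higher than LAB. Assumed here because it is not stated: a two-sided comparison of two group means.

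**1. Reproducing the 23%.** Normal approximation with a common SD: (1.960 + 0.842) × √(2/6) × 0.1445 = 2.802 × 0.5774 × 0.1445 = 23.4%. This agrees with the stated 23%.

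**2. The same calculation by t-test.** With 10 degrees of freedom the two-sided critical value is 2.228. For 80% power the noncentral t distribution needs a standardised difference of about 1.796, and 1.796 × 0.1445 = 26.0%. Variants of the detectable difference, as a share of the HAB mean:

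- t-test, common SD, n = 6: 26.0%
- t-test, common SD, n = 5: 29.3%
- t-test, variance pooled over three groups of six (15 df): 25.0%
- t-test, n = 6, SD proportional to each group's mean: 23.1%

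At a true difference of 23% (0.23/0.1445 = 1.591 SD), power with n = 6 is 70.1% by the common-SD t-test, 78.7% by the normal approximation and 79.5% by the proportional-SD t-test.

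**3. Which method the protocol probably used.** Section 12 introduces the lung calculation as similar to the one for brain, so the brain figures are a check. There the mean is 4.5, the SD 1.4, n = 10, and the stated result is 40%. The normal approximation gives 39.0%, the t-test 41.2% with a common SD and 40.4% with pooled variance. The proportional-SD t-test gives 34.8%, which does not match. The normal approximation is the one method tried that comes close to both stated figures.

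**4. The benchmark on the HAB base.** LAB mean = 25.6/1.27 = 20.16. Gap = 25.6 − 20.16 = 5.44 SUV·min. As a share of the HAB mean, 5.44/25.6 = 21.3% (equivalently 1 − 1/1.27). In SD units, 5.44/3.7 = 1.471; the noncentrality is 1.471 × √(6/2) = 2.548.

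| Two-sided method, n = 6 | Power at 21.3% |
|---|---|
| t-test, common SD | 63.3% |
| t-test, variance pooled over three groups | 66.4% |
| Normal approximation: Φ(2.548 − 1.960) | 72.2% |
| t-test, SD proportional to mean | 72.3% |

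With five per group the common-SD t-test gives about 53%. If 27% is misread as a share of the HAB mean, the same test at n = 6 gives 83%.

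**5. The significance threshold.** The smallest observed difference that reaches two-sided p<0.05, with an observed SD of 3.7, is 2.228 × √(2/6) × 0.1445 = 18.6% of the HAB mean. The 23% is a true difference to be detected with 80% probability, which is a different quantity.

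**The case against.** A reader might infer that 23% is an arithmetic error. It is not. It reproduces by a standard formula, and a t-test in which the SD shrinks in proportion to the mean gives almost the same value. The protocol does reason in terms of SD/mean. However, its stated assumption is that the ratio is similar between the two ligands, not between genotypes, and that method does not reproduce the brain figure. What stands is that 26% depends on a common SD and that 23% is optimistic rather than wrong.

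A reader might also infer that the protocol promises 80% power for the PK 11195 effect and delivers 63%. It makes no such promise: 80% is claimed at 23% only, and no effect size is hypothesised for ER176. The 63% is the low end of a range that reaches 72% among two-sided methods. A one-sided test would give 77% (t) to 82% (normal), but the protocol does not state one.

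A third tempting reading is that the lung component has no allowance for withdrawals, because half of 12 is exactly the six that were powered. Section 6.i says about half and lets the share vary with the quality of the results, so six is not a fixed count.

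Finally, an SD from five subjects is itself very uncertain. Under normality its 95% interval is about 2.2 to 10.6 SUV·min, which moves the normal-approximation detectable difference from about 14% to 67%. A gap between 23% and 26% is small against that. This lowers the severity. It does not excuse the mixed bases, since the benchmark falls below 23% whatever the SD.

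**Conclusion.** The point holds with moderate severity. The mixed bases are the firmest part: 27% on the LAB mean is 21.3% on the HAB mean, below the protocol's own 23%, and this needs no assumption about the test. Power for a difference of that size with six per group is about 63% to 72% in the two-sided variants, so roughly 28% to 37% of such studies would miss it. The detectable difference is 26% rather than 23% for a two-sided t-test with a common SD of 3.7, and power at 23% is then about 70%. Reading 23% as the threshold for significance is mistaken: on the same inputs the threshold is about 18.6%.

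All these power figures take the PK 11195 SD/mean ratio as valid for ER176, as the protocol does. Lung uptake is a secondary outcome, and the protocol attaches no decision rule to the 23%. The consequence is a risk of over-reading a null lung result, not a threat to the primary brain or dosimetry aims.

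**What to change.** In section 12, state the test and sidedness behind the lung figure and replace the conclusion with wording such as:

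> With six subjects per group, a two-sided t-test has 80% power for a true difference of about 26% of the HAB mean (29% with five). The HAB–LAB difference seen with PK 11195 is 21.3% of the HAB mean, for which power is about 63–72%. A non-significant lung result therefore does not exclude a genotype effect of the size seen with PK 11195.

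Delete the sentence that makes 23% the difference needed for significance.

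The cost is rewording only; no subjects, scans or procedures change. Giving more of the planned 12 per genotype a lung scan is optional and not part of this fix. By the common-SD t-test, 80% power needs eight per group at 23% and nine at 21.3%, and each added lung scan interrupts a brain acquisition that serves the primary outcome.

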13. HUMAN SUBJECTS PROTECTION

13A Subject selection

Participants will be selected based upon their meeting the study's eligibility criteria. Participants will be admitted to the protocol regardless of their age, gender, race or ethnicity.

13B Justification for exclusion of children

Since this protocol has more than minimal risk from radiation exposure without possibility of direct benefit, inclusion of children is not appropriate.

13C Justification for the exclusion of vulnerable subjects

Pregnant women will be excluded because this protocol involves exposure to ionizing radiation.

Lactating women will be excluded because radioisotopes may be excreted in milk.

13D Justification for the exclusion of persons with HIV/AIDS or brain disease

This protocol studies only healthy volunteers. Persons with brain disease and HIV infection are excluded because such diseases are likely to be associated with a disruption of the blood-brain barrier or a viral infection of the brain which can alter the levels of translocator protein, the biomarker imaged in the current study.

13E Safeguards for Vulnerable Populations

Pregnancy testing will be performed before PET and MRI scanning for any participants of child-bearing potential.

13F Qualifications of investigators

[name], MD, PhD, has more than 10 years experience using nuclear imaging. [name] is a clinical authorized user (CAU) of radioisotopes and a credentialed physician. His responsibilities include study design, recruiting healthy subjects, consenting subjects, participating in PET scanning procedures, data analyses, and interpretation and publication of study results.

[name], PhD will be the associate investigator for this study. He completed his MD program from India and a PhD program in PET molecular imaging in Japan. His responsibilities include but are not limited to study design, participating in PET scanning protocols, data analyses, and interpretation and publication of study results. He will not obtain informed consent.

[name] and [name] RN, CRNP are credentialed nurse practitioners. Their responsibilities include recruiting healthy subjects, patient evaluation and care, consenting subjects, participating in PET scanning procedures.

14. BENEFITS

Participants participating in this protocol receive no direct benefit. Information obtained from this protocol study may improve our understanding of the pharmacokinetics of a new TSPO tracer.

15. SUMMARY/CLASSIFICATION OF RISK

This study entails more than minimal risk with no prospect of direct benefit to participants. The risks are reasonable in relation to anticipated benefit.

16. CONSENT DOCUMENTS AND PROCESS

The consent forms contain all required elements. There are two different consent forms submitted with the present protocol to scan healthy subjects: for brain imaging with arterial line, and for dosimetry.

The investigators designated in section #13 above will obtain informed consent. Each subject will receive an oral and written explanation of the purposes, procedures, and risks of this study in a language appropriate for the individual's level of understanding. Participants will have the opportunity to carefully review the written consent form and ask questions regarding this study prior to signing the document. A member of the protocol team will be available to answer questions about the study to be performed. A copy of the signed consent form will be placed in the medical record, and a copy will be given to each study participant.

If a non-English speaking participant is unexpectedly eligible for enrollment, the CC standard short written consent form in the appropriate language and a written summary of what the Investigator will say to the participant will be used as part of an oral consent process. The IRB approved English written consent form will serve as the written summary if the short form process is used. The investigator will obtain an interpreter unless the investigator is fluent in the prospective participant's language. Preferably, the interpreter will be someone who is independent of the participant (i.e., not a family member). Interpreters will be found through the Department of Social Work. The interpreters will translate the current IRB-approved English version of the consent verbatim and facilitate discussion between the participant and investigator.

The written summary will be signed by the investigator obtaining consent and a witness to the oral presentation. The short written consent form will be signed by the participant and a witness who observed the presentation of information. The interpreter may sign the consent document as the witness and, in this case, will note "Interpreter" under the signature line. A copy of the signed form will be provided to the participant to take home.

The investigator obtaining consent will document the consent process in the participant's medical record, including the name of the interpreter. Further, all instances of use of the short form process will be reported to the IRB at the time of annual review.

17. QUALITY ASSURANCE

1. QA Monitor: [name]

The PI will ensure that:

- the protocol is being correctly followed
- changes to the protocol have been approved by the IRB
- accurate, complete, and current records are being maintained and are secure
- subject withdrawal or study failure is noted in the records and
- informed consent has been correctly documented

The QA audit committee will conduct periodic monitoring of the protocol.

2. QA Plan:

This protocol will undergo periodic review by the QA audit committee as outlined in the NIMH QA SOPs.

18. DATA AND SAFETY MONITORING

1.Data and safety monitor

The PI is responsible for data and safety monitoring for this protocol and will review the data every 6 months.

2.Data and safety monitoring plan

The PI will review the ongoing investigation every 6 months. The PI will monitor safety aspects of the study as a whole to make sure that the frequency of adverse events including serious adverse events and unanticipated problems are within expectations.

3.Criteria for stopping the study or suspending enrollment or procedures In the event of a serious adverse event related to the research, or if new data shed light on the danger of any procedures used, the study team, including the PI, will suspend further testing, until the IRB and investigators have reviewed the safety information and make a determination about whether to continue the study.

19. ADVERSE EVENT AND UNANTICIPATED PROBLEM REPORTING

The Principal Investigator is responsible for detecting, documenting, and reporting unanticipated problems, adverse events (AEs), including serious adverse events (SAEs), and

deviations in accordance with NIH policy, IRB requirements, and federal regulations. Relatedness to the research of all serious adverse events will be determined by the PI in consultation with the CD. Serious unanticipated problems and serious protocol deviations will be reported to the IRB and CD as soon as possible and in writing on the Problem Report Form not more than 7 days after the PI first learns of the event. Not serious unanticipated problems and not serious deviations will be reported to the IRB and CD as soon as possible and in writing on the Problem Report Form not more than 14 days after the PI first learns of the event.

Deaths will be reported to the Clinical Director within 7 days after the PI first learns of the event.

All adverse events, deviations, and unanticipated problems will be summarized and reported at the time of Continuing Review.

20. ALTERNATIVES TO PARTICIPATION

Subjects participating in this protocol will not receive any treatment in this study or forego any treatment in order to participate in this study. The alternative, therefore, is not to participate.

21. CONFIDENTIALITY

1. Medical Records

Protocol consents and other medical information will be maintained in the participant's NIH medical record.

2. Research Data

All medical information collected from study participants will be kept in a locked file at the NIH Clinical Center, or password protected computers in secured rooms. Unique identifiers without personally identifying information will be used to label all data. Strict standards of confidentiality will be upheld at all times.

3. Stored Samples

Blood samples will be discarded at the end of the study. All data will be stored under password-protected accounts accessible only to the principle investigator and directly involved study personnel to preserve subject privacy.

22. CONFLICT OF INTEREST

A use-patent application will be submitted for the use of [¹¹C]ER176. The possibility does exist for the principle investigator, the medically responsible investigator and the NIMH to benefit financially from the results of this protocol.

23. TECHNOLOGY TRANSFER

There is no technology transfer agreement for this study.

24. RESEARCH AND TRAVEL COMPENSATION

Volunteers will be compensated for time and research-related inconveniences. Reimbursement is based on NIH standards for time devoted to the research project.

Participants will be paid for each portion of the study they have completed whether or not they opt for early withdrawal from participation. The total compensation will be up to \$370

	Total Pay
Visit 1 to NIH (outpatient) (For	
Brain imaging i.e. Phase 1 only)	
MRI	\$100
Pregnancy test	\$10
Visit 2 to NIH (outpatient)	
PET scanning	\$150
Arterial catheter	\$60
Antecubital venous catheters	\$30
Pregnancy test	\$10
Movement restriction	\$10
Total	\$370

For dosimetry studies, the MRI and its relative pregnancy test, and the arterial catheter placement will not be done. Therefore only two visits to the NIH will be necessary and the total compensation will be \$200.

NIH will cover travel expenses to the Clinical Center for all participants in accord with NIH guidelines.

